5.5 Describe the procedure for obtaining intervention group assignment

The study coordinator with the statistician will randomize participants stratified by MCI status. Participants with and without MCI will be randomized in a 1:1 ratio to either piano training or the active control condition of music listening instruction. To ensure balance throughout enrollment, randomization will be stratified by MCI status (present vs. absent) and conducted in varying blocks of participants as designed by Co-I Ji. [name] will generate the stratified permuted random blocks using R. [name] will maintain the random seed and the computer codes and will send the randomization list to the clinical trial coordinator. The treatment allocation will be denoted as A or B and recorded on the randomization form by the clinical trial coordinator. The study coordinator will control access to the randomization list and know whether A (B) stands for intervention (control). Study investigators [name], [name], and [name] will remain blind to participant condition. The testers will remain blind to participant condition. The trainers (including Co-I [name]) and clinical trial coordinator will be aware of participants' randomized condition.

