6 CLINICAL AND LABORATORY EVALUATIONS

Schedule of Evaluations

Evaluation	Measure type	Telephone Screening (≤ 60 days)	Baseline	Clinical Evaluation (≤ 45 days)	Randomization ≤3 wks	Intervention Up to 15 wks	Post-Test >2 days and ≤60 days
Informed Consent	R		X				
Inclusion/Exclusion Questionnaire	I/E	X	X	X			X
Geriatric Depression Scale (GDS)	I/E, C		X				
Demographic Data	C		X				
Montreal Cognitive Assessment (MoCA)	I/E, C		X				
Memory Screening History	IV		X				
Hearing and vision screening Pure-tone Hearing Thresholds Speech Recognition Threshold Near Visual Acuity	I/E, C		X				X
Music Reading Assessment	I/E		X				
Central Auditory Processing Time Compressed Speech 65% Words-in-Noise Test Dichotic Digits Test Dichotic Sentence Identification test ATTR	O		X				X

08/08/2018

Evaluation	Measure type	Telephone Screening (≤ 60 days)	Baseline	Clinical Evaluation (≤ 45 days)	Randomization ≤3 wks	Intervention Up to 15 wks	Post-Test >2 days and ≤60 days
Cognitive Assessment Battery Trail Making Test Digit Coding Verbal Fluency - BHR, Clothes/ Girls' Names, Vegetables/ Musical Instruments (baseline) - FAS, Animals/ Boys' Names, Fruits/Furniture (post-test)	O		X				X
Everyday Functional Assessment Timed IADL Test Test of Everyday Attention	O		X				X
Questionnaires Health Questionnaire Medication Audit Health Changes	SC		X X				X
Adverse Events	R		X	X		X	X
Clinical Evaluation NACC assessments: -Clinical Dementia Rating Scale -Craft Story 21 Recall - Immediate and De- layed -Benson Complex Figure Copy and recall -Multilingual Naming Test -Functional Assessment Scale -Clinician Diagnosis form	SC			X			

08/08/2018

Evaluation	Measure type	Telephone Screening (≤ 60 days)	Baseline	Clinical Evaluation (≤ 45 days)	Randomization ≤3 wks	Intervention Up to 15 wks	Post-Test >2 days and ≤60 days
Lab Assessments (upon IRB approval) CBC Metabolic panel Thyroid Stimulating Hormone (TSH) B12 D Folic Acid MRI (if funding acquired)	IV			X			
Randomization	IV				X		
Advanced Measures of Music Audiation (AMMA)- Day 1 of Training	E					X	
Basic Piano Measure (BPM) OR Music Listening Measure (MLM)- At days 1 and 20 of training	E					X	
General Self-Efficacy and Music Performance Self-Efficacy (At days 1 and 20 of training)	E					X	
Intervention sessions	C					X	
NICT Expectations Questionnaire (Between days 17 and 20 of training)	IV, C					X	
Tester blinding assessment	IV						X

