C=covariate, E=exploratory, I/E=inclusion/exclusion, IV=internal validity, O=outcome, R=regulatory, SC=sample characterization							

6.1 *Timing of Evaluations*

Prior to Randomization: The baseline visit should be scheduled within 60 days of the telephone screening interview. Informed consent must be obtained first at the baseline study visit prior to any data collection. The GDS, MoCA, Music Reading Assessment, as well as hearing and vision screenings must be completed at baseline, prior to the clinical evaluation. The central auditory processing measures, cognitive assessment battery, everyday functional assessments and health questionnaire should be completed at baseline, but missing items can be administered at the beginning of the clinical evaluation, if needed. The clinical evaluation should be completed within 45 days of the baseline visit completion. The NACC assessments will be completed at the clinical evaluation. All the aforementioned measures for the baseline and clinical evaluations should be completed prior to randomization and must be completed prior to the training content being administered. It will be allowable to administer any of the aforementioned measures that are missing from the baseline or clinical visits after randomization, but administration will not be allowed once the participant has received any piano or music listening training.

Prior to Training Content: Any biomarker assessments must be completed prior to training content (blooddraw, mri, etc.). The general and music self efficacy measures can be administered at either baseline or after randomization on day 1 of training, but must be administered prior to participants receiving any piano- or music listening- content training. If the basic piano or music listening measures are administered prior to randomization, the participant will be withdrawn from the trial and a protocol deviation will be noted. The pre-training basic piano and music listening measures must be administered after randomization and must be administered before training content is delivered. If any of the aforementioned baseline, clinical, or pre-training measures are administered after the training content began, a protocol deviation will be noted. Such measures will be coded as missing and will not be used in analyses.

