6.1.2 Intervention Phase

Within three weeks of baseline or clinical evaluation phase completion for each replicate, the Clinical Research Coordinator and/or Research Assistant Trainers will randomize enrolled participants in collaboration with [name] and schedule their first intervention visit. Participants will complete randomized exercises in groups of up to 10 individuals at in-lab sessions that are 90 minutes in duration, occurring two times a week over the subsequent ~3 months. The goal will be for 95% of the training sessions to be conducted in groups of 3-10 persons. Clas-

ses will be arranged such that those with MCI primarily train together within randomized condition. The intervention phase will continue until 20 total sessions are completed or 15 weeks have passed. The trainers will confirm or reschedule the participant to complete an immediate post-intervention assessment. The trainers will make certain that all scheduled intervention sessions are completed prior to the post-test visit and that no training sessions are scheduled after the post-test visit. Fidelity will be assured as described below (See **Quality Assurance** below).

At the first training sessions the trainers will administer the Advanced Measure of Music Audiation (AMMA), General Self-Efficacy Form, and the Music Performance Self-Efficacy form. Those in the music listening control group will complete the music listening measure while those in piano training will complete the basic piano measure. The training protocols detail all of the procedures and content protocols detail the training arms. Please see: P:\CBCS\CSD CAL\Study 15 Music Training NIA\Trainer Docs\Study 15 Music Training procedure protocol.

Between sessions 17 and 20, the trainers will administer the The Cognitive Training Expectations NICT questionnaire to examine participants' attitudes and expectations about the potential effects of the intervention completed. If a participant does not complete this questionnaire during the intervention phase, it may be completed at the beginning of the post-test visit.

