An adapted version of the Music Performance Self-Efficacy Measure¹²⁰ will be used. This questionnaire ($\alpha=.97$) consists of 24 items to which participants respond by selecting a number (0–100) to reflect strength of agreement to a specific statement regarding musical beliefs (0 = strongly disagree ... 100 = strongly agree). The items included are based on Bandura's sociocognitive theory and assess domains: mastery experiences (eight items), vicarious experiences (five items), verbal/social persuasion (six items), and physiological state (five items). An example of an item from this measure is, "I have had positive experiences performing music in the past." This measure has been used in studies with older adults¹²¹. The adaptation from the original version includes a change in the order of the questions and changes in the wording of 7 questions. More specifically, the question, "I have improved my music performance skills by watching professional musicians, who are similar to me in some way, perform well", was changed to "I have improved my music performance skills by watching professional musicians perform well". The question, "My friends think I am a good performer on my primary instrument", was changed to "My friends think I am a good performer on my piano". The question, "I have had positive experiences performing in large ensembles" was changed to "I have had positive experiences performing in large ensembles (more than 11 performers)". The question, "I have improved my music performance skills by watching other students, who are similar to me in some way, perform well" was changed to "I have improved my music performance skills by watching someone I know perform well (parent, brother, sister, church member, etc.)". The question "I have had positive experiences performing solo, or, in a small ensemble" was changed to "I have had positive experiences performing music solo". The question, "I have had positive

experiences performing music in large ensembles” was changed to “ I have had positive experiences performing music in a small ensemble (2-10 performers)”. Lastly, the question “Performing with my instrument makes me feel good” was changed to “Performing on piano makes me feel good”.

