The self-efficacy measures (general self-efficacy and music performance self-efficacy) will be examined as exploratory outcomes by comparing the two randomized conditions across the two measurement points (before/after training). Analyses will include ordinal logistic regression analyses across levels of self-efficacy conducted within the generalized estimating equations (GEE) statistical framework to account for repeated measurements. Significant improvements on either measures demonstrated in this analyses will be followed by exploratory mediation analyses to examine if improvements in self-efficacy can account for any observed training

effects on CAP, cognition, or everyday function. Thus, we will examine an alternative hypothesis that training gains can be attributed to improved self-efficacy. An alpha of .05 will be used.

To explore if initial music aptitude affects performance within each of the training conditions, AMMA at baseline will be examined as a covariate (i.e., modifier) of Basic Piano Measure performance (BPM) from the first to the final day of training among those in the piano training condition. Similarly, baseline AMMA will be examined as a covariate on the Music Listening Measure (MLM) across the same two time points within the control group. Again, ordinal logistic regression with GEE will be used given the ordinal scaling of the outcomes. An alpha of .05 will be used.

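### The pre-training self-efficacy scores are routinely taken after randomization by trainers who know the arm, so the exploratory before/after comparison and mediation test rest on a baseline open to influence from assignment

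*Combined protocol and SAP*

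**What the plan says.** Section 6.1 (Prior to Training Content) offers two time points for the pre-training General Self-Efficacy and Music Performance Self-Efficacy forms: "The general and music self efficacy measures can be administered at either baseline or after randomization on day 1 of training". Its one restriction concerns training content: "but must be administered prior to participants receiving any piano- or music listening- content training".

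The Schedule of Evaluations in section 6 lists only the later option, "General Self-Efficacy and Music Performance Self-Efficacy (At days 1 and 20 of training", marks it in the intervention column and types it as exploratory. Section 6.1.2 matches the schedule: at the first training sessions "the trainers will administer the Advanced Measure of Music Audiation (AMMA), General Self-Efficacy Form, and the Music Performance Self-Efficacy form". Section 5.5 adds: "The trainers (including Co-I [name]) and clinical trial coordinator will be aware of participants' randomized condition".

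Under section 5.7, participants are scheduled into classes by randomized condition, and both arms are described to them as music training. At the first training sessions the piano arm also takes the Basic Piano Measure and the control arm the Music Listening Measure (section 6.1.2). The plan does not fix the order of these measures relative to the self-efficacy forms.

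Section 9.8 analyses self-efficacy by "comparing the two randomized conditions across the two measurement points (before/after training", using ordinal logistic regression within GEE at alpha .05. If improvement is significant, exploratory mediation analyses follow, to see whether self-efficacy could account for any training effects on central auditory processing, cognition or everyday function.

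**The concern.** A randomized before/after comparison relies on a before score that assignment cannot have changed. Self-efficacy is a self-reported belief. Someone who has just found out that they will learn the piano, or that they will not, may answer differently from the same person a few weeks earlier. If the form is completed after that moment, part of the effect of assignment sits in the before score and is subtracted from the change.

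An upward shift in the piano arm could hide a real gain in self-efficacy and keep the mediation analysis from being triggered. A downward shift could produce an apparent gain that did not arise from training. Because either time point is allowed, one variable may also combine scores with different meanings, and section 9.8 has no adjustment or sensitivity analysis for time of administration.

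**Working it through.** **Timing rules side by side**

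| Place | When the before form is given | Who gives it |
|---|---|---|
| 6.1 | Baseline visit or day 1, before any content | Not stated |
| Schedule of Evaluations | Day 1 only | Not stated |
| 6.1.2 | First training sessions | Trainers |
| 5.5 | – | Trainers know the arm |

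Post-randomization collection is therefore the operational default. The restriction in 6.1 protects against exposure to content, not against knowledge of the arm. That trainers know the arm is stated. That participants know it on day 1 is an inference from classes formed by arm and arm-specific tests at the first sessions.

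**Size of the possible effect**

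The plan gives no figure on this point to reproduce, so this is an illustration in baseline-SD units with a normal approximation. The planned model is ordinal GEE.

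Inputs:
- n = 99 per arm (section 9.3), alpha .05 (section 9.8), taken as two-sided.
- b, the shift in one arm's before score on learning the arm. Assumed 0 to 0.3 SD.
- ρ, the before/after correlation. Assumed 0.5 to 0.8. Section 6.3.5 gives only internal consistency for these scales.

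Formulas, for a shift in the piano arm and a true between-arm difference Δ:
- Change score: expected estimate Δ − b; SE = √(2(1−ρ))·√(2/99).
- Before score as covariate: expected estimate Δ − ρ·b; SE = √(1−ρ²)·√(2/99).
- Rejection rate: 1 − Φ(1.96 − d/SE) + Φ(−1.96 − d/SE), where d is the expected estimate.

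Example for the change score with ρ = 0.5, b = 0.2, Δ = 0: SE = 1 × 0.142 = 0.142; |d|/SE = 0.2/0.142 = 1.41; rejection rate 0.291.

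Results, with ranges over ρ = 0.5 to 0.8:

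| b | Change: bias | Change: rejection if Δ = 0 | Change: rejection if Δ = 0.25 | Covariate: bias | Covariate: rejection if Δ = 0 | Covariate: rejection if Δ = 0.25 |
|---|---|---|---|---|---|---|
| 0 | 0 | 0.050 | 0.420–0.794 | 0 | 0.050 | 0.528–0.834 |
| 0.1 | −0.1 | 0.108–0.199 | 0.184–0.386 | −0.05 to −0.08 | 0.069–0.155 | 0.369–0.513 |
| 0.2 | −0.2 | 0.291–0.604 | 0.064–0.086 | −0.10 to −0.16 | 0.128–0.467 | 0.184–0.230 |
| 0.3 | −0.3 | 0.560–0.916 | 0.064–0.086* | −0.15 to −0.24 | 0.230–0.804 | 0.052–0.128 |

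*The expected estimate here is 0.25 − 0.3 = −0.05, so its sign is reversed.

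The table assumes that everyone in the shifted arm is measured on day 1. If only a fraction p is, the average shift is p·b; for example, p = 0.5 and b = 0.2 gives 0.1. With every score taken before randomization, b = 0 and the first row applies.

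**The case against.** The best defence is that a score taken after allocation but before content isolates change during training and lies closer to its start. The clinical evaluation may come 45 days after baseline (section 6.1), and section 6.2 asks for at least two weeks between the end of the baseline/clinical phase and training. For someone evaluated on day 45 the gap is at least 45 + 14 = 59 days. This is a real cost of baseline measurement. But section 9.8 frames the analysis as a comparison of randomized conditions, and for that purpose a score taken before allocation is the safer reference. The plan does not say that it intends the narrower question.

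Two other points stand in part. The scales are self-report, so trainers do not score them and the main route is the participant's own reaction. The shared music-training label gives some masking, though it is unlikely to survive a first session in a piano or listening class. Section 6.1.2 also names the self-efficacy forms before the piano and listening measures, but it does not set that order as a rule.

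Some stronger readings are tempting but not supported:
- **That the baseline is contaminated.** The documents show the opportunity. No self-efficacy data are reported.
- **That the expectations gap in section 14 (5.55 versus 4.99) shows a reaction to assignment.** That questionnaire was planned for sessions 17 to 20 or the start of post-test. It follows weeks of different training, measures expectations, and says nothing about day 1.
- **That section 6.1 would already code day-1 scores as missing.** It does so only for measures given after training content began. It even allows missing baseline outcome measures to be completed after randomization. For those outcomes this is an allowance for missing items; for self-efficacy, day 1 is the schedule.
- **That the music scale is piano-worded and so unusable across arms.** Section 6.3.5 describes seven reworded items out of 24, and two of them name the piano, one being "Performing on piano makes me feel good". That is too little to set the scale aside.

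**Conclusion.** The point holds as a minor design weakness in an exploratory analysis. The before self-efficacy score is open to influence from knowledge of assignment and may mix pre- and post-randomization values, and the analysis takes no account of either.

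The bias equals the average shift in SD units for a change score, and ρ times that shift if the before score is a covariate. The covariate form would apply if the self-efficacy mediation follows the general approach in section 9.6. A shift of 0.1 to 0.2 SD would be enough to distort the test, but whether any shift occurred, in which direction and how large, is not in the documents. The values of b and ρ are assumptions, and the linear illustration stands in for an ordinal model.

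A reader might infer that the trial's main results are in doubt. They are not. The measures are exploratory, and no primary or secondary conclusion depends on them. Section 14 reports no significant group-by-time interaction on any outcome (all p > .194), which leaves little training effect for self-efficacy to explain.

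**What to change.** In the Schedule of Evaluations and sections 6.1 and 6.1.2, give both self-efficacy forms at the baseline visit before randomization, as 6.1 already permits. Allow day 1 only as a recorded fallback, completed before the piano or listening measure. In section 9.8, add a sensitivity analysis limited to participants whose before score predates randomization. Whether a participant has such a score is settled before allocation, so the randomized comparison is kept within that subset.

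Section 14 states that data collection ended in April 2021. For the existing data, report when each before score was taken, run the sensitivity analysis if any pre-randomization scores exist, and attach a caveat to the self-efficacy results.

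The cost is small. Two forms with 23 + 24 = 47 items move to the baseline visit, which becomes slightly longer. Some forms will be collected from people who are never randomized, and the gap between the before score and the start of training grows.

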6.1.1 Pre-Randomization Evaluations

Telephone screening is an initial interview conducted by Cognitive and Neurophysiology of Aging Lab staff to ascertain potential eligibility of the participants per the inclusion and exclusion criteria. Eligibility will be evaluated by the telephone screening. If ineligible the reason will be documented. Procedures for eligibility and enrollment are detailed above. Those potentially eligible will be scheduled to complete a baseline visit within 30 days. If the telephone screening questionnaire has not been completed within 60 days of scheduling baseline, it should be repeated.

A subject ID number will be assigned on the participants visit control sheet (VCS) by the tester at their first study visit. Informed consent will be obtained at the beginning of the first-in person visit, the baseline visit. Participants will be provided a flow chart that explains all of the study visits, duration of the visits, and the timing of the visits during the consent process. At the baseline visit, participants will complete the MoCA, GDS, hearing, and vision screenings, and MRA to determine eligibility. Those not eligible due to MoCA, GDS, hearing or vision scores will be referred to the appropriate professionals for treatment. Additionally, participants for whom outer or middle ear pathology is indicated through otoscopic examination will be referred to an otolaryngologist or other professional and will not continue in the study. Those participants who are eligible will be enrolled in the study and will further complete thorough assessments of CAP, cognition, and everyday function. A questionnaire assessing health will be completed. Research Assistant Testers who will remain blind to participant condition will complete these assessments. Participants will be referred to the study coordinator for randomization.

If the participant meets eligibility criteria, was not referred from the MDC or a study physician, but scores between 20-25 on the MoCA, a clinical evaluation will be performed by a study physician to ascertain diagnosis of mild cognitive impairment and ensure that clinical inclusion criteria are met and no exclusion criteria are evident. Reasons for ineligibility will be documented. This clinical evaluation should be completed as soon as possible following the baseline visit and should take place within 45 days after the baseline visit.

